5.1.1.4.3 Clinical Laboratory Assessments

Clinical laboratory assessments will be summarized by treatment group for the Safety Population as follows:

Table 5-19 Clinical Laboratory Summaries

Type of Endpoint	Description	Timing	Methodology
Laboratory values over time	Summary by laboratory category and parameter in SI units and analysis visit 
 • Parameters specified in Section 6.6.2.2 	Part 1: Screening, Baseline (Day 1), Months 1, 3, 6, 9, 12, and 30-Day Follow-up, Early DC ¹ Part 2 (subjects newly randomized in Part 2): Screening, Baseline, Months 1, 6, 12 Part 2 (all subjects (continuing from Part 1 and newly randomized in Part 2): Every 6 months from Month 18 through Month 96 End of Study Part 1 and Part 2: Follow-up, Early Discontinuation Visit ¹	CFB descriptive statistics
Laboratory abnormalities by toxicity grade	Summary by laboratory category and parameter 
 • Grade 1, Grade 2, Grade 3 and Grade 4 categories based on NCI CTCAE version 4.03 • Parameters specified in Table 6-8 • Include all post-baseline combined for counts of toxicity by grade. Only treatment-emergent laboratory abnormalities should be summarized in laboratory abnormalities by grade – must have a toxicity that is a higher grade than at baseline to be included.	Part 1: Screening, Baseline (Day 1), Months 1, 3, 6, 9, 12, and 30-Day Follow-up, Early DC ¹ Part 2 (subjects newly randomized in Part 2): Screening, Baseline, Months 1, 6, 12 Part 2 (all subjects (continuing from Part 1 and newly randomized in Part 2): Every 6 months from Month 18 through Month 96 End of Study Part 1 and Part 2: Follow-up, Early Discontinuation Visit ¹	Categorical descriptive statistics

¹ Based on nominal visits defined in the schedule of assessments.

5.1.1.4.3.1 Liver Biochemistry

Elevations of ALP, ALT, AST, or bilirubin, or confirmed ALP, ALT, AST, or bilirubin elevations (with or without liver-related clinical symptoms) will be summarized by treatment group for the Safety Population as follows:

Table 5-20 Liver Biochemistry Summaries

Type of Endpoint	Description	Timing	Methodology
ALP, ALT, AST, or bilirubin elevations with or without liver-related clinical symptoms	ALP, ALT, AST, or bilirubin elevations with or without liver-related clinical symptoms (with or without confirmatory measurement), based on protocol Table 11-1	Treatment Period + 30 days after treatment end date	Categorical descriptive statistics
Confirmed ALP, ALT, AST, or bilirubin elevations with or without liver-related clinical symptoms	Confirmation of ALP, ALT, AST, or bilirubin elevations based on protocol Table 11-1. Confirmatory measurements are obtained <3 days, 3-5 days, or >5 days; adjudication decisions are classified as unlikely, possible, and probable DILI (drug-induced liver injury).	Treatment Period + 30 days after treatment end date	Categorical descriptive statistics

ALP = alkaline phosphatase; ALT = alanine aminotransferase; AST = aspartate aminotransferase

5.1.1.4.4 Vital Signs

Vital signs will be summarized by treatment group and in total for the Safety Population as follows:

Table 5-21 Vital Signs Summaries

Type of Endpoint	Description	Timing	Methodology
Vital signs over time	Summary by parameter and analysis visit 
 Parameters specified in Section 6.6.3.2 	Part 1: Screening, Baseline, Treatment Period (Months 1, 3, 6, 9, 12), 30-Day FU, Early DC Part 2 (subjects newly randomized): Screening, Baseline, Treatment (Months 1, 6, 12) Part 2 (all subjects – continuing from Part 1 and newly randomized in Part 2): Through to Month 60 biopsy, Post biopsy, EOS, 1-Month FU, Early DC ¹	CFB descriptive statistics

¹ Based on nominal visits defined in the schedule of assessments.

5.1.1.4.5 Electrocardiograms

Electrocardiograms (ECGs) will be summarized by treatment group and in total for the Safety Population as follows:

Table 5-22 ECG Summaries

Type of Endpoint	Description	Timing	Methodology
ECG parameter values over time	Summary by parameter and analysis visit 
 Parameters specified in Section 6.6.4.3 	Part 1: Baseline, Treatment Period: Month 12 Part 2: (subjects newly randomized): Baseline, Treatment Period: Month 12 Part 2 (all subjects –continuing from Part 1 and newly randomized in Part 2): Through to Month 60 Biopsy, and Post biopsy ¹	CFB descriptive statistics

¹ Based on nominal visits defined in the schedule of assessments.

5.1.1.4.6 Other Analyses

Not applicable.

5.1.1.5 Subgroup Analyses

In Part 1, subgroup analyses for the primary efficacy endpoint using the CMH test will be reported for selected subgroups to be defined in this section (table below). These analyses will place emphasis on the comparison of CVC to placebo within subgroups and assessing the consistency of magnitude of the treatment effect across subgroups. The odds ratios from the CMH analysis will be reported with associated 2-sided 95% CIs.

In addition, subgroup analyses will be conducted for the key secondary endpoint and secondary endpoints for NASH CRN fibrosis stage (2 vs. 3) and for T2DM at baseline (yes, no) (based upon the data entries in the electronic database).

Subgroup results (treatment effect estimate and two-sided 95% CIs) will be presented on a Forest plot also displaying the overall treatment effect and its 95% CI. The emphasis will be on assessing the consistency of the treatment effect across subgroups, i.e., overlapping CIs indicate consistent treatment effects.

The table below also displays the rationale for pre-specifying the specific subgroup i.e. regulatory requirements to assess consistency of effect for major demographic factors (e.g., age, sex, and race or ethnicity), [REDACTED]

[figure not shown]
For some subgroups, detailed information with many levels are collected (e.g., race/ethnicity); frequencies of subjects for each separate subgroup level will be reported as part of the demographic and baseline characteristics summaries. However, to provide an assessment of the consistency of efficacy and safety results across major subgroup categories, some levels will be combined into 3 to 4 major categories for each subgroup. This will ensure that the number of subjects per category is sufficient to perform meaningful subgroup analyses.

[figure not shown]
The list of subgroups may be modified depending on the recruitment to the trial to ensure the number of subjects is sufficient in the subgroups to be assessed. This will be determined before unblinding.

[figure not shown]
Table 5-23 Subgroups

[figure not shown]
Subgroup	Categories	Comments
Age at baseline (years)	< 65, ≥ 65	
Sex	Male, Female	
Race	White, Non-white	
NASH CRN fibrosis stage at baseline	2, 3	Data from Phase 2b to be confirmed or refuted. To be based on the true data (e.g., as reported in the CRF rather than in IxRS)

Subgroup	Categories	Comments
Geographic region	USA only EU only USA/Canada vs. Rest of World (ROW) ROW: 
 • EU • Australia/New Zealand • Middle East/Africa • Asia Pacific (excluding Australia/New Zealand) • Latin America (Mexico, Central and South Americas) (Note: a full list of countries will be compiled after enrolment of Part 1 is complete and before unblinding of Part 1, and each will be assigned to a geographic region. Additional countries added after unblinding of Part 1, if any, will be assigned to a geographic region for analysis of Part 2.)	

5.1.1.6 Interim Analyses

5.1.1.6.1 Part 1 Analyses

The Part 1 analyses will occur when approximately 1200 randomized subjects have been followed through the Month 12 visit assessment. Subjects who will contribute to the primary analysis of Part 1 will be identified before unblinding of any subjects for Part 1 analysis.

To perform the Part I analyses, an unblinded team will be identified whose members will be unblinded to the treatment information at the individual subject level. The unblinded team members will no longer be involved in any ongoing daily conduct of the blinded study in Part 2. Other blinded personnel will assume or continue their responsibilities until the end of Part 2.

or study team members who will not continue activities subsequent to the Part 1 lock. Individual subjects' treatment group assignments will not be disseminated to the sites until the end of Part 2 to allow for continued blinded assessment during Part 2.

5.1.1.6.2 Data and Safety Monitoring Board

An independent DSMB will be formed to review ongoing data from this study. The DSMB will be composed of members who have medical expertise in liver disease and at least one statistician. The DSMB will be empowered to recommend changes to the protocol to ensure the safety of subjects in the study but will not be empowered to recommend stopping or changing the study due to accumulating efficacy data, other than at the planned futility analysis in Part 2 of the study.

Safety data will be reviewed by the DSMB. The first review will occur after the first subject has been followed for at least 6 months. Subsequent reviews will be at least quarterly, at a schedule agreed by the sponsor and the members of the board per the DSMB charter. This data review will not result in any adjustments to alpha because there will not be a chance to stop the study early for a conclusion of efficacy.

For Part 2 of the study, one unblinded assessment of futility may be performed by the DSMB. This may occur after the last randomized subject has been followed for at least 2 years and at least half of the expected events have been observed. If the conditional power exceeds 5%, the study will continue. The study will be stopped only for a conclusion of futility. This data review will not result in any adjustments to alpha because there will not be a chance to stop the study early for a conclusion of efficacy.

No investigator or subject will be unblinded to support DSMB review. No one involved in data review or subject care will be unblinded.

5.1.1.6.3 Adjudication Committee

An independent adjudication committee will be formed to review all events which are potentially components of the primary composite endpoint for Part 2 of the study. Only events confirmed by the adjudication committee will be included in the analysis of the primary endpoint of Part 2; the time to onset will be determined as the date on which the event occurred according to the adjudication committee.

5.1.2 Determination of Sample Size

Part 1:

The sample size for the primary endpoint of Part 1 is based on the primary binary endpoint at the end of Month 12 comparing treatment with CVC versus placebo. The planned sample size of 1200 subjects (800 in treatment Arm A and 400 in treatment Arm B) for Part 1 of this study is expected to provide 84% power to demonstrate strong evidence with a single study (2-sided alpha level of 0.0012), assuming a 15% response rate for the placebo arm and a 25% response rate for CVC according to the results from the Phase 2b Study 652-2-203 (CENTAUR).

The planned 800 subjects in treatment Arm A and 400 subjects in treatment Arm B is expected to provide 97% power to demonstrate strong evidence with a single study (2-sided alpha level of 0.0012) in the key secondary endpoint, assuming a 2.2% response rate for the placebo arm and an 8.6% response rate for CVC according to the results from the Phase 2b Study 652-2-203 (CENTAUR).

PASS 8.0 is used to calculate the sample size.

These response rates reflect the primary analysis, in which subjects missing the post-baseline liver biopsy will be included as nonresponders.

The anticipated proportion of subjects with missing Month 12 liver biopsies, as a result of either premature subject discontinuation or nonevaluable liver biopsy results (i.e., biopsy sample deemed inadequate for evaluation of efficacy endpoints by an independent central pathologist), is estimated to be 15% of subjects at Month 12, compared to approximately 13% of missing post-treatment liver biopsies in the Phase 2b study.

Part 2:

The sample size for the primary endpoint analysis in Part 2 is based on the estimated event-free survival rate of 80% for the placebo group and detection of a hazard ratio of 0.62 by the anticipated end of the study at Month 60 (corresponding to a median event-free survival time of approximately 15 years for placebo and 25 years for CVC). A total of 2000 subjects (2:1 randomization ratio between CVC and placebo) enrolled approximately uniformly over 2 years for an overall study duration of approximately 8 years (2 years of accrual period plus 5 to 6 years of follow-up) will lead to about 367 events, after accounting for an overall dropout rate of 20%. With these events, there will be 85% power to demonstrate strong evidence of superiority of CVC over placebo (at a 2-sided 0.00125 significance level, for a single registration study), and 99% power to test the superiority of CVC over placebo (at the 2-sided test 0.05 significance level for a registration study).

EAST 6.4 is used for the calculation.

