## **12.8. Sample Size and Power**

### **12.8.1. Part 1**

The sample size for the primary endpoint of Part 1 is based on the primary binary endpoint at the end of Month 12 comparing treatment with CVC versus placebo. The planned sample size of 1200 subjects (800 in treatment Arm A and 400 in treatment Arm B) for Part 1 of this study is expected to provide 84% power to demonstrate strong evidence with a single study (2-sided alpha level of 0.0012), assuming a 15% response rate for the placebo arm and a 25% response rate for CVC according to the results from the Phase 2b Study 652-2-203 (CENTAUR).

The planned 800 subjects in treatment Arm A and 400 subjects in treatment Arm B is expected to provide 97% power to demonstrate strong evidence with a single study (2-sided alpha level of 0.0012) in the key secondary endpoint, assuming a 2.2% response rate for the placebo arm and an 8.6% response rate for CVC according to the results from the Phase 2b Study 652-2-203 (CENTAUR).

PASS 8.0 was used to calculate the sample size.

These response rates reflect the primary analysis, in which subjects missing the postbaseline liver biopsy will be included as nonresponders. The anticipated proportion of subjects with missing Month 12 liver biopsies, as a result of either premature subject discontinuation or nonevaluable liver biopsy results (ie, biopsy sample deemed inadequate for evaluation of efficacy endpoints by an independent central pathologist), is estimated to be 15% of subjects at Month 12, compared to approximately 13% of missing post-treatment liver biopsies in the Phase 2b study.

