
Primary
 
 To demonstrate the superiority of CVC compared to placebo on liver histology at Month 12 relative to the Screening biopsy 	
Primary Endpoint
 
 Improvement in fibrosis by at least 2 stages (NASH CRN system) AND no worsening of steatohepatitis (no worsening of lobular inflammation or hepatocellular ballooning grade 2005) on liver histology at Month 12 relative to Screening biopsy

Key Secondary None
	
Key Secondary Endpoint None

Secondary
 

	
Secondary Endpoints
 

EU Part 2:

Objectives: EU Part 2	Endpoints: EU Part 2
Primary Same as global objectives	Primary Endpoint Same as global endpoint

[figure not shown]

[figure not shown]

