Part 2: Primary efficacy endpoint: Time to first occurrence of adjudicated events	Date of Baseline visit will be used in the calculation for time to first occurrence of any of the following adjudicated event endpoints: 
 • Death (all cause) • Histopathologic progression to cirrhosis (based on NASH CRN fibrosis stage 4) • Liver transplant • MELD score ≥ 15 • Ascites (requiring intervention, i.e., large volume paracentesis $\geq 1L$ or initiation of a diuretic) • Hospitalization (as defined by a stay of ≥ 24 hours) for onset of: variceal bleed, hepatic encephalopathy (defined by a West Haven Stage of ≥ 2), spontaneous bacterial peritonitis (confirmed by diagnostic paracentesis with positive ascitic fluid bacterial culture) If any of the adjudicated events occur in Part 1, they will be included in the primary efficacy endpoint for Part 2.	For subjects newly randomized in Part 2: Date of Baseline visit in Part 2 For subjects continuing from Part 1: Date of Baseline visit in Part 1

Type of Endpoint	Description	Timing
Part 2: Secondary efficacy endpoint (for subjects newly randomized in Part 2): Improvement of fibrosis stage (NASH CRN system) on liver histology at Month 12 relative to the Screening biopsy	Fibrosis stage (NASH CRN system) based on Screening biopsy.	Screening biopsy result before Baseline visit and before subject is randomized in Part 2
Part 2: Secondary efficacy endpoint (for subjects newly randomized in Part 2): Worsening of steatohepatitis (no worsening of lobular inflammation or hepatocellular ballooning grade 2005) on liver histology at Month 12 relative to the Screening biopsy	NAFLD activity score (NAS) components based on Screening biopsy.	Screening biopsy result before Baseline visit and before subject is randomized in Part 2

5.1.1.3.1 Endpoint Domain 1

The testing hierarchy is as follows for the Part 1 analyses:

[figure not shown]
- Global: Part 1 testing hierarchy includes 2 tests, one for the primary endpoint and the other for the key secondary endpoint, which are both binary endpoints. The key secondary endpoint is tested only when the primary endpoint result is significant. These surrogate endpoints will be tested at the 0.0012 (2-sided) alpha level to manifest strong evidence from a single confirmatory study, and 0.048 (2-sided) level for study success.

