- Region-specific Europe: Part 1 testing is only for the region-specific primary endpoint, a binary endpoint. The surrogate endpoint will be tested at the 0.0012 (2-sided) alpha level to manifest strong evidence from a single confirmatory study, and 0.048 (2-sided) level for study success.

The general description of the domains of clinically-related endpoints is stated below.

Table 5-14 Domain 1 Analyses

Type of Endpoint	Description	Timing	Methodology
Part 1: Primary efficacy endpoint (binary)	
For the primary efficacy analysis in Part 1, using the mITT analysis set, any available liver biopsy after baseline will be used as the Month 12 biopsy, no matter when it was obtained relative to the first dose of study drug. Subjects who do not have an evaluable liver biopsy at both Screening and Month 12 will be included in the analyses as nonresponders. Subjects with multiple liver biopsies will have the evaluable biopsy closest to the Month 12 visit included in the analysis.
 
The proportion of subjects who meet the primary efficacy endpoint in Part 1, and the proportion who meet each component of the primary efficacy endpoint, will be summarized by treatment group. Two-sided 95% CIs for the proportion of subjects who meet the primary efficacy endpoint, calculated using Wilson's method for CI, will be reported.
 
Analysis of the primary and key secondary endpoints of Part 1 will use the Cochran-Mantel-Haenszel (CMH) test, stratified by true fibrosis stage (2, 3) and T2DM status (presence, absence) at baseline, for a total of 4 strata, to compare the rates in the 2 randomized treatment arms.
	
Screening, Month 12
 
The primary analysis of Part 1 will occur when approximately 1200 randomized subjects have been followed for at least 12 months. Subjects who will contribute to the primary analysis of Part 1 will be identified before unblinding of any subjects for Part 1 analysis; subjects who will not contribute to the primary analysis of Part 1 will be identified by date of randomization. Individual subjects' treatment group assignments will not be disseminated to the sites until the end of Part 2 to allow for continued blinded assessment during Part 2.
	
Responder
 
Two-sided 95% CIs for responder using Wilson's method for CI.
 
Cochran-Mantel-Haenszel (CMH) test, stratified by true fibrosis stage (2, 3) and T2DM status (presence, absence) at baseline

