5.1.1.3.3 Multiple Comparisons Procedure for Primary and Secondary Endpoints

The significance level of both 0.00125 (2-sided) and 0.05 (2-sided) will be applied to hypothesis testing in this study, with the former to manifest strong evidence from a single confirmatory study and the latter for study success. Alpha splitting will be applied for multiplicity adjustment. The above applies for both global and EU-specific analyses.

To manifest strong evidence from a single confirmatory study, the familywise type I error rate (between the surrogate endpoint and the clinical outcome endpoint) will be controlled at the 0.00125 level by initial assignment of 0.0012 to the surrogate endpoint and 0.00005 to the clinical outcome endpoint, and the clinical outcome endpoint will be tested at the 0.00125 level if the tests of the surrogate endpoints (i.e., primary and key secondary) are successful. The testing procedure will be the same for study success, except the familywise type I error rate will be controlled at the 0.05 level instead of 0.00125 level, in which an initial alpha level of 0.048 to the surrogate endpoint and of 0.002 to the clinical outcome endpoint will be allocated.

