5.2 Changes in the Conduct of the Study or Planned Analyses

5.2.1 Changes in the Conduct of the Study

Approximately 1200 randomized participants were planned for the Part 1 analyses. During the actual study execution during the screening period for Part 1, 1293 participants were randomized into Part 1. This affects the newly randomized subject enrollment numbers anticipated for Part 2, as the number newly randomized in Part 2 will be decreased from approximately 800 to approximately 707. However, the total number randomized remains the same:

Arm	Newly Randomized Subjects in Part 2 N	Total Subjects (Randomized in Part 1 or Part 2) N	Treatment
A	472	1334	CVC 150 mg, once daily
B	235	666	Placebo, once daily

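### The stated Part 1 powers of 84% and 97% do not match the planned CMH test, and the 97% ignores the gate on the global key secondary endpoint

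*SAP*

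**What the plan says.** Protocol 12.8.1 states that 1200 subjects, 800 on CVC and 400 on placebo, are "expected to provide 84% power to demonstrate strong evidence with a single study (2-sided alpha level of 0.0012), assuming a 15% response rate" on placebo and 25% on CVC. SAP 5.1.2 repeats this and adds that the same numbers are "expected to provide 97% power to demonstrate strong evidence with a single study (2-sided alpha level of 0.0012) in the key secondary endpoint", with assumed rates of 2.2% and 8.6%. Both sections name PASS 8.0 but neither the test nor the variance behind the figures. Missing biopsies are already counted as non-response in these rates, so no further allowance is needed.

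On the analysis, SAP Table 5-14 says: "Analysis of the primary and key secondary endpoints of Part 1 will use the Cochran-Mantel-Haenszel (CMH) test", with four strata. For the global analysis, SAP 5.1.1.3.1 adds: "The key secondary endpoint is tested only when the primary endpoint result is significant". For Europe the same section says that "Part 1 testing is only for the region-specific primary endpoint, a binary endpoint". SAP 4.2 defines that EU endpoint as "Improvement in fibrosis by at least 2 stages (NASH CRN system) AND no worsening of steatohepatitis", which is the global key secondary endpoint.

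SAP 5.2.1 reports that "1293 participants were randomized into Part 1". The power statement in 5.1.2 is still for 1200.

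**The concern.** There are two separate issues.

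- **Variance.** The CMH statistic is standardised by its variance under the null hypothesis. With 2:1 allocation and the higher expected rate in the larger arm, that variance exceeds the unpooled one. A power taken from the unpooled formula is therefore too high for the planned test.
- **Gate.** The 97% is the power of the key secondary taken alone. In the global plan that test happens only if the primary has succeeded at the same level. Even on the plan's own numbers, the chance of showing the key secondary in the stated order cannot exceed 84%.

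What is at stake is the risk a reader attaches to the endpoint of at least 2 stages at the strong-evidence level. It is the global key secondary and the sole EU Part 1 primary.

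**Working it through.** **Inputs.** From SAP 5.1.2: 800/400 subjects, 2-sided alpha 0.0012 (z = 3.239), rates 15% v 25% (primary) and 2.2% v 8.6% (at least 2 stages). From the table in SAP 5.2.1, Part 1 arm sizes by subtraction: 1334 − 472 = 862 CVC and 666 − 235 = 431 placebo, which sum to 1293 and are exactly 2:1.

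**1. Reproducing the stated figures.** Unpooled z-test: power = Φ(d/SE₁ − z), with SE₁ = √[p₀(1−p₀)/n₀ + p₁(1−p₁)/n₁].

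- Primary: SE₁ = 0.02352; Φ(0.10/0.02352 − 3.239) = Φ(1.013) = 0.8445.
- At least 2 stages: SE₁ = 0.01233; Φ(0.064/0.01233 − 3.239) = Φ(1.951) = 0.9745.

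These match 84% and 97%. Other common forms at 800/400 (primary / at least 2 stages) are further off:

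- pooled variance: 78.2% / 89.2%
- pooled with continuity correction: 75.7% / 86.0%
- arcsine: 80.9% / 94.7%
- unpooled with continuity correction: 82.5% / 96.4%

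**2. The same inputs with the null variance.** Power ≈ Φ((d − z·SE₀)/SE₁), with SE₀ = √[p̄(1−p̄)(1/n₀ + 1/n₁)].

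- Primary: p̄ = 0.2167, SE₀ = 0.02523; Φ((0.10 − 3.239 × 0.02523)/0.02352) = 0.7816.
- At least 2 stages: p̄ = 0.0647, SE₀ = 0.01506; Φ((0.064 − 3.239 × 0.01506)/0.01233) = 0.8915.

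The normal approximation is rough at rates this low, so the single-stratum CMH statistic was also evaluated by exact binomial enumeration (first two columns below).

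**3. Through the global gate.** A responder by at least 2 stages without worsening is also a responder by at least 1 stage without worsening. The endpoints are nested, so with equal rates across strata the stated rates fix the joint distribution and no outside correlation is needed. The last column comes from 400,000 simulated trials.

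| CMH, 2-sided 0.0012, equal rates across strata | Primary | At least 2 stages, alone | Both, in the global order |
|---|---|---|---|
| 800/400 (planned) | 0.7846 | 0.9098 | 0.738 |
| 862/431 (1293 randomised) | 0.8288 | 0.9395 | 0.796 |

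A separate simulation of the four-stratum CMH test with equal rates gave the same results to within 0.2 points.

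**4. Different rates by stratum.** The documents give no stratum rates. Assumed here: two equal strata with rates at the stated multiples of the mean, 862/431, 200,000 trials.

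| Rates relative to mean | Primary | At least 2 stages, alone | Both |
|---|---|---|---|
| 0.7 / 1.3 | 0.841 | 0.940 | 0.807 |
| 0.6 / 1.4 | 0.852 | 0.942 | 0.819 |
| 0.4 / 1.6 | 0.879 | 0.949 | 0.846 |

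**5. Study-success level (0.048).** Primary, at least 2 stages alone, and both: 98.3%, 99.8% and 98.2% at 800/400; 98.9%, 99.9% and 98.8% at 862/431.

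**The case against.** The strongest reply is that nothing was miscalculated. The stated figures reproduce from the stated inputs, and they are per-endpoint powers at a planned size of 1200. Quoting per-endpoint power inside a hierarchy is common, and the gate is stated openly elsewhere. Of the 17-point difference for the global key secondary at 1293, about 3 points (97% to 94%) come from the test and about 14 (94% to 80%) from asking for the power in sequence. That decomposition is right and is kept apart here. It does not rescue the figures, because the planned test does not deliver 84% and 97% at 1200 even one endpoint at a time. That PASS was run with the unpooled test is an inference from the fit.

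A second reply is that the differences are small beside the uncertainty in the assumed rates. At 862/431 the CMH power for the primary runs from 71% to 91% as the CVC rate moves from 24% to 26%. For the endpoint of at least 2 stages it runs from 88% to 97% as the CVC rate moves from 8.0% to 9.2%. This is true, but it is no reason to leave a figure that does not belong to the planned test.

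Two smaller points stand. The 862/431 split is derived from target totals rather than reported arm counts, so the text should say that 2:1 is assumed. The efficacy set is mITT, so a few subjects may drop out; with 1% never dosed the figures become 82.5%, 93.6% and 78.9%. Finally, Part 1 is already randomised and type I error is unaffected, so this is a correction to the text and not to the design.

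**Conclusion.** The concern holds. At the planned 1200 the CMH test gives about 78% and 91%, roughly 6 points below each stated figure, and about 74% for the key secondary through its gate. At 1293 the primary is at about 83%, so over-enrolment has nearly restored it. What remains is the endpoint of at least 2 stages: about 94% alone, which is the right figure for the EU primary, and about 80% in the global order. The risk of not showing it at 0.0012 is therefore about 6% (EU) or 20% (global), against the 3% implied by 97%.

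This rests on the plan's own response rates, a 2:1 split of 1293 and equal rates across strata. The assumed stratum differences can lift the primary to 84% or above, but they leave the endpoint of at least 2 stages at no more than about 95% alone and 85% through the gate. The effect is confined to the strong-evidence level.

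**What to change.** Restate SAP 5.1.2, naming the test. Suggested wording:

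> With 1293 subjects randomised (862 CVC and 431 placebo, assuming 2:1) and the stratified CMH test at 2-sided 0.0012, assuming equal response rates across strata, power is about 83% for improvement by at least 1 stage and about 94% for improvement by at least 2 stages tested alone (the EU primary). In the global hierarchy the power to show both is about 80%.

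If 1200 is kept as the planning size, the corresponding figures are 78%, 91% and 74%.

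The cost is a few sentences. Enrolment, alpha and analyses stay as they are. At 1293 the stated power falls by about 1 point for the primary, 3 for the EU primary and 17 for the gated global key secondary; at 1200 the falls are about 6, 6 and 23 points.

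A separate and optional addition concerns Part 2. Its stated 85% applies once the full 0.00125 has been released. With 367 events, a hazard ratio of 0.62 and 2:1 allocation, the Schoenfeld formula gives Φ(√(367 × 2/9) × |ln 0.62| − z) = Φ(4.317 − 3.227) = 0.862 at 0.00125, and Φ(4.317 − 4.056) = 0.603 at 0.00005. Before adding this, reconcile the release rule. SAP 5.1.1.3.3 releases the alpha "if the tests of the surrogate endpoints (i.e., primary and key secondary) are successful", whereas the Protocol synopsis, Protocol 12.3.2.2 and SAP Table 5-14 refer to a single surrogate test. An averaged Part 2 power should not be stated.
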